Nothing herein is to be disclosed in any way without the prior express written permission of W. L. Gore & Associates, Inc.

Post-market study: Evaluation of the GORE® VIABAHN® Endoprosthesis for the treatment of Popliteal Artery Aneurysm

Protocol number: FPR 14-03

Protocol date: 14-JULY-2015

NCT number: NCT02462876

W. L. Gore & Associates, Inc.
Medical Products Division

CONFIDENTIAL INFORMATION

MD133246 Protocol Template

Revision#: 5

Doc Type: GC

Page 1 of 1

Nothing herein is to be disclosed in any way without the prior
express written permission of W. L. Gore & Associates, Inc.

Post-market study: Evaluation of the GORE® VIABAHN® Endoprosthesis
for the treatment of Popliteal Artery Aneurysm

Protocol Number: FPR 14-03

Amendment 1: 14 July 2015

W. L. Gore & Associates, Inc.
Medical Products Division

CONFIDENTIAL INFORMATION

MD133246 Protocol Template
Revision#: **1MD134619.docx**
Doc Type: GC

PROTOCOL SUMMARY

Study Title	Post-market study: Evaluation of the GORE® VIABAHN® Endoprosthesis for the treatment of Popliteal Artery Aneurysm
Protocol Number	FPR 14-03
Sponsor	W. L. Gore & Associates, Inc. Medical Products Division [name] United States [contact]
Study Medical Device	GORE® VIABAHN® Endoprosthesis; CE marked medical device
Study Design	This is a French multicenter, non-randomized, single arm, retrospective Post-market study with a prospective follow-up of GORE® VIABAHN® Endoprosthesis for the treatment of Popliteal Artery Aneurysm (PAA).
Study Objective	The primary objective is to document the long term safety and performance of the GORE® VIABAHN® Endoprosthesis for the treatment of patients with Popliteal Artery Aneurysms.
Study Endpoints	
The primary performance endpoint for this trial is:
 
 • Primary patency at 12 months 
The primary safety endpoint of this trial is:
 
 • 12 month serious adverse events and adverse events related to the study procedure or the study device. 
The secondary endpoints of this trial are:
 
 • Serious adverse events and adverse events related to the study procedure or the study device at 24 & 36 months; • Freedom from limb loss on the study limb through 12, 24 & 36 months; • Freedom from repeat intervention at 12, 24 & 36 months; • Length of hospital stay after procedure in days; • Length of procedure in minutes; • Primary patency at 24 & 36 months; • Primary assisted patency at 12, 24 & 36 months; • Secondary patency at 12, 24 & 36 months. • Technical Success 
Listings:

CONFIDENTIAL INFORMATION

	Listings of the following events will be provided: endoleak, migration, device fracture, and study limb amputation.
Subject Population	The study population includes patients with a symptomatic aneurysm or asymptomatic aneurysm (≥ 2 cm diameter) of the popliteal artery, or presence of mural thrombus (< 2 cm) in the popliteal artery. All patients treated per IFU with the GORE® VIABAHN® Endoprosthesis since September 15, 2012 (date of reimbursement in France) will be screened consecutively, starting with the first patient treated.
Number of Patients	Patients meeting Inclusion / Exclusion that provided Informed Consent will be enrolled in consecutive order. 50 patients with adequate follow-up to determine primary endpoints through 12 months will be enrolled. For patients that cannot be enrolled, but had a PAA treated with VIABAHN in the respective time, the date of the intervention and the reasons for non-inclusion will be collected in a screen-failure CRF.
Number of Sites	Up to 10 Sites in France.
Expected Time to Complete Enrollment	Patient identification / enrollment is expected to take up to 9 months. Patients follow-up will continue to collect 36 months data.
Schedule of Events	All patients will be followed up as per hospital standard of care for the duration of the study. As available, data will be collected on adverse events, ankle brachial index, palpable pedal pulses, medications, imaging, all re-interventions, and bypass surgeries.

1.1. Disease

Popliteal Artery Aneurysms (PAAs) are the most prevalent type of peripheral arterial aneurysm, accounting for 70 to 85% of all peripheral aneurysms with an overall prevalence of about 0.1% in hospitalized patients. At most, this corresponds to four or five patients per year at any major vascular center in the United States (U.S.).[1-9] The popliteal artery is considered aneurysmal once the diameter reaches either 1.5 cm or 1.5 times the size of the normal proximal artery. PAAs occur much more frequently in men than in women; reports range from approximately one woman to every fifteen men to one woman to every thirty men.[4, 8, 10-14] PAA incidence increases with age and approximately one-half of PAAs are bilateral.[5, 13, 15] Studies have reported that an abdominal aortic aneurysm (AAA) is found in 9 to 64% of PAA patients [5, 7, 12, 13, 15, 16] and about the same proportion have hypertension.[12, 13, 15] The primary risk of PAA is generating thromboemboli that can occlude downstream vasculature and compromise lower limb tissue (leading to acute limb ischemia).[17, 18] Acute limb ischemia is often the first presenting symptom in patients with PAA. When a PAA is detected and treated with medical management, complication rates are high (15-25% at one year, 60-75% at five years).[19] Studies have suggested that the risk of complication is greatest in aneurysms larger than 2 cm, but that even smaller aneurysms with mural thrombus can lead to distal embolization.[1, 5, 20]

Depending on the aneurysm, symptoms may include local pain, swelling or severe pulsation but the most frequent and severe symptoms of PAA are thromboembolism and thrombosis, which can lead to claudication, acute limb ischemia and major amputation. Symptomatic PAAs (i.e., claudicant or ischemic limb) account for approximately 40% of diagnosed PAAs and carry a risk of major amputation as high as 30-40%.[13, 16, 20, 21] The risk of thromboembolic complications in untreated, asymptomatic PAA ranges from 24% at one year to 74% at five years.[5, 22] Although PAAs expand at a growth rate of around 10% per year [23], rupture is rare with an annual occurrence rate of 1.4%.[15]

Duplex ultrasound is the most useful test to confirm the diagnosis of PAAs and can also accurately measure the size of the aneurysm, document thrombosis, including intraluminal thrombus, and assess for compression of adjacent veins. Duplex ultrasound can be supplemented with computed tomography or conventional arteriography if surgery is planned. The goal of PAA repair is to exclude the popliteal aneurysm and maintain or re-establish arterial downstream inflow.[24] There is general consensus that all symptomatic PAAs should be repaired regardless of size and asymptomatic PAAs are recommended to be treated if the aneurysm diameter is greater than 2 cm, mural thrombus is present or the patient has poor run-off.[1, 25]

1.2. Historical Treatments

The current gold standard of PAA repair is saphenous vein bypass grafting with either ligation (most common) or endoaneurysmorrhaphy (resection of the aneurysm).[16, 26] When ligation is used, up to a third of bypassed aneurysms may continue to enlarge due to the presence of geniculate arteries that feed the aneurysm.[27, 28] Vein bypass is generally used in the majority of patients.[2, 16]

When no suitable vein conduit is available, expanded polytetrafluoroethylene (ePTFE) grafts are typically used, with reported primary patencies up to 30% lower than vein bypass at five

CONFIDENTIAL INFORMATION

MD133246 Protocol Template

Revision#: 1

Doc Type: GC

and ten years.[2, 16] In general, clinical outcomes are also negatively influenced by the presence of pre-operative ischemic symptoms and poor run-off regardless of the type of revascularization procedure performed.[2, 14, 29, 30] Although reported outcomes vary widely due to inconsistent patient populations as well as treatment and patency definitions, most studies report bypass graft patency of 69–80% at five years and limb salvage rates between 75–100%.[3, 14, 15, 25, 31, 32] In these published studies, patency and limb salvage rates tend to be better in asymptomatic patients.

Several recent reports have advocated endovascular treatment of PAAs over surgical repair.[17, 33-36] Endovascular treatment provides shorter operative times; shorter hospital stays with less perioperative morbidity and faster recovery.[3, 22, 33, 37-39]

The first report of endovascular PAA repair was published in 1994, in which a vascular graft was sewn to two balloon-expandable stents and then deployed.[40] Since then, many different approaches to endovascular PAA repair have been reported, including both stented grafts (ePTFE, vein or Dacron grafts attached to balloon-expandable stents) and commercial Dacron stent-grafts. Early outcomes with these devices were mixed, primarily due to high rates of thrombosis and mechanical failure.[21, 36, 41-44] More recent studies report the use of the GORE® VIABAHN® Endoprosthesis manufactured by W. L. Gore & Associates, Inc. (Gore) to treat PAAs with long-term clinical outcomes comparable to traditional surgical bypass.[4, 6, 18, 33, 39, 45-47] With its lower morbidity and mortality, endovascular repair provides an option for patients who are not surgical candidates due to existing comorbidities.[24] Importantly, physicians may choose to intervene on asymptomatic patients earlier (prior to thromboembolic events) without precluding surgical bypass at a later date.[24, 48] As described above, the main goal of treatment is to prevent distal embolization and acute limb ischemia.

1.3. Study Device Description

The GORE® VIABAHN® Endoprosthesis is a flexible, self-expanding endoluminal endoprosthesis consisting of an ePTFE lining with an external nitinol (NiTi=Nickel: Titanium) support extending along its entire length (Figure 1). Having a CE mark since 1996, the GORE® VIABAHN® Endoprosthesis is a flexible, self-expanding endoluminal prosthesis for endovascular grafting of peripheral arteries. The intent of the device in this Post-market study is to exclude the PAA from the blood flow.

[figure not shown]

Figure 1. GORE® VIABAHN® Endoprosthesis

[figure not shown]

Figure 2. Dual Lumen Delivery Catheter

Available sizes of the GORE® VIABAHN® Endoprosthesis can be found in Table 1.

CONFIDENTIAL INFORMATION

MD133246 Protocol Template

Revision#: 1

Doc Type: GC

[REDACTED]

[REDACTED]	[REDACTED]	[REDACTED]
[REDACTED]	[REDACTED]	[REDACTED]
[REDACTED]	[REDACTED]	[REDACTED]
[REDACTED]	[REDACTED]	[REDACTED]
[REDACTED]	[REDACTED]	[REDACTED]
[REDACTED]	[REDACTED]	[REDACTED]
[REDACTED]	[REDACTED]	[REDACTED]
[REDACTED]	[REDACTED]	[REDACTED]
[REDACTED]	[REDACTED]	[REDACTED]
[REDACTED]	[REDACTED]	[REDACTED]

1.4. Clinical Data

[REDACTED]

Publications in recognized peer reviewed journals regarding the use of GORE® VIABAHN® Endoprosthesis in PAAs are available since 2006 and as of today clinical data relating to more than 400 study limbs with follow-up of more than 10 years can be found in the literature.

1.4.1. Overall Data Review

A summary of published data from 16 studies in which the GORE® VIABAHN® Endoprosthesis was used to treat over 400 limbs (34 limbs were treated with alternate stent-grafts) is presented in Table 2.

Table 2. Summary of Clinical Data from Endovascular Repair of PAAs

Author	Year	Limbs	[REDACTED]	Latest Follow-up (year)	[REDACTED]	Study Type	[REDACTED]
Mohan [18]	2006	30 ^a	[REDACTED]	3	[REDACTED]	Retrospective, Multicenter	[REDACTED]
Rajasinghe [37]	2007	23	[REDACTED]	1	[REDACTED]	Retrospective, Single Center	[REDACTED]
Antonello [33]	2007	21	[REDACTED]	6	[REDACTED]	Prospective, Randomized, Comparative, Single Center	[REDACTED]

Author	Year	Limbs	[REDACTED]	Latest Follow-up (year)	[REDACTED]	Study Type	[REDACTED]
Ghotbi [45]	2007	27	[REDACTED]	4	[REDACTED]	Prospective, Single Center	[REDACTED]
Thomazinho [47]	2008	11	[REDACTED]	1.7	[REDACTED]	Prospective, Single Center	[REDACTED]
Maru [50]	2008	50	[REDACTED]	2	[REDACTED]	Retrospective, Multicenter	[REDACTED]
Idelchik [51]	2009	33 ^b	[REDACTED]	4.5	[REDACTED]	Prospective, Single Center	[REDACTED]
Tielliu [35]	2010	78	[REDACTED]	10	[REDACTED]	Retrospective, Single Center	[REDACTED]
Ascher [52]	2010	15	[REDACTED]	2.5	[REDACTED]	Prospective, Single Center	[REDACTED]
Etezadi [53]	2010	18	[REDACTED]	0.5	[REDACTED]	Retrospective, Single Center	[REDACTED]
Jung [46]	2010	15	[REDACTED]	6	[REDACTED]	Retrospective, Single Center	[REDACTED]
Le [54]	2010	21	[REDACTED]	0.6	[REDACTED]	Retrospective, Single Center	[REDACTED]
Kim [39]	2010	24	[REDACTED]	1	[REDACTED]	Retrospective, Single Center	[REDACTED]
Midy [4]	2010	57 ^c	[REDACTED]	3	[REDACTED]	Retrospective, Multicenter	[REDACTED]
Garg [63]	2012	26	[REDACTED]	2	[REDACTED]	Retrospective, Single Center	[REDACTED]
Pulli [62]	2013	134	[REDACTED]	4	[REDACTED]	Retrospective, Multicenter	[REDACTED]

[REDACTED]

[REDACTED]

[REDACTED]

In the majority of the studies, the physician chose to repair aneurysms that were either symptomatic or had aneurysm diameter either greater than 2 cm in diameter or greater than 1.5 times the healthy native vessel.

CONFIDENTIAL INFORMATION

2.2. Secondary Objectives

The secondary objectives of the GORE® VIABAHN® Endoprosthesis Popliteal Artery Aneurysm study are to document long-term (through 36 months) safety and performance by evaluating freedom from limb loss, length of hospital stay after study procedure, length of study procedure, serious adverse events (SAEs), device or procedure related adverse events (AEs), technical success, primary patency, primary assisted patency, secondary patency and freedom repeat intervention. In addition, listings of device migration, endoleak, device fracture, and study limb amputation will be reported separately.

3. Study Design

3.1. Study Design Schema

The study design is depicted in Figure 3 below.

CONFIDENTIAL INFORMATION

MD133246 Protocol Template

Revision#: 1

Doc Type: GC

[figure not shown]

Figure 3. Study Design Schema

CONFIDENTIAL INFORMATION

3.2. Description of Study Design

This is a retrospective, multicenter, non-randomized single-arm clinical study with a prospective follow-up to evaluate the safety and performance of the GORE® VIABAHN® Endoprosthesis for the treatment of patients with PAAs. All patients will have received the GORE® VIABAHN® Endoprosthesis for treatment of a PAA since September 15, 2012 (date at which reimbursement for the GORE® VIABAHN® device was received in France). Inclusion for all patients will be retrospective, follow-up visit(s) can be prospective.

A maximum of 10 Clinical Investigative Sites (referred to as “Sites” in the remainder of this document) in France will participate in this study. 50 patients with an adequate follow-up to assess primary endpoints will be enrolled. All patients will have received the GORE® VIABAHN® Endoprosthesis for treatment of a PAA since 15 September 2012 and meet all of the inclusion and none of the exclusion criteria as specified in Sections 4.2 and 4.3 of this protocol.

Data entry will be monitored and enrollment will be stopped when 50 subjects have data for the 12 months follow-up visit entered.

Patients with bilateral PAAs treated with GORE® VIABAHN® Endoprosthesis at different dates can be enrolled in the study. The first limb enrolled will be considered the study limb. Patients with both limbs treated within the same procedure will not be enrolled in the study.

Follow-up examinations through 12 months (+/- 3 months) post-implant will be collected for the primary endpoint analysis. This will include clinical assessment, imaging-based evaluations, SAEs, device, and procedure related AEs. Patients will be further followed through 24 and 36 months post-procedure.

3.3. Study Endpoints

3.3.1. Definitions

Acute Limb Ischemia[55]: Defined by the operating or treating physician. Typically defined as emergently threatened, whether marginally or immediately, implying reversible ischemia in a limb that is salvageable without a major amputation if arterial obstruction is relieved quickly or irreversible ischemic change requiring major amputation.

Adverse Event (AE): Any untoward medical occurrences, unintended disease or injury or any untoward clinical signs (including abnormal laboratory findings) in patients, users or other persons related to the investigational medical device or procedure.[56] For this study, only device or procedure related AEs need to be reported.

Device Fracture: A stent fracture was defined as any discontinuity of the normal structure of the stent as diagnosed on x-ray.

Endoleak (Modified from White et al.)[57]:

Type I – Present when a persistent perigraft channel of blood flow develops due to inadequate or ineffective seal at the graft ends.

Type II – Occurs when there is persistent collateral blood flow into the aneurysm sac flowing retrogradely from collateral branches.

Type III – Arises at the mid-graft region due to leakage through a defect in the graft fabric or between the segments of multiple grafts.

Type IV –Blood diffusion across the pores of the graft fabric or through tiny holes in the graft fabric caused by sutures or stent struts.

Type V - Leakage from an unknown origin.

Hinge Point: Located at the adductor tubercle, which corresponds to the upper border of the patella, in a plane perpendicular to the femoral axis.

Length of Hospital Stay: The number of days the subject remains in the hospital due to endovascular repair of a PAA with VIABAHN (“index procedure”).

Length of Procedure: The number of minutes the subject remains in the operating room or catheterization laboratory due to endovascular repair of a PAA. If no specific information is available the first and last angiographic timestamp can be used to capture the length of the procedure.

Limb Loss: An amputation on the study limb above the metatarsals.

Migration: Any post-operative device migration requiring treatment.

Patency:

Primary Patency: Blood flow without occlusion maintained through the device after implant without an intervention.

Primary Assisted Patency: Blood flow maintained through the device after implant regardless of re-interventions performed (without occlusion).

Secondary Patency: Blood flow through the device regardless of re-interventions performed (with or without occlusion) and freedom from surgical bypass.

Re-intervention: Endovascular or surgical procedure performed to treat a stenosis or occlusion within the study device(s) or within 5 mm of the proximal or distal edge of the device(s), treatment of endoleaks or other reasons.

Serious Adverse Event (SAE)[56]: An AE that led to death or lead to serious deterioration in the health of the subject that resulted in a life threatening illness or injury, or a permanent impairment of a body structure of body function, or in-patient or prolonged hospitalization, or a medical or surgical intervention to prevent life-threatening illness or injury, or permanent impairment to a body structure or a body function.

Technical Success: Successful aneurysmal exclusion using the GORE® VIABAHN® Endoprosthesis at time of the procedure without Type I or III endoleaks that require post-procedure intervention within 30 days.

3.3.2. Primary Endpoints

The primary performance endpoint for this trial is:

- Primary patency at 12 months.

The primary safety endpoint for this trial is:

- Serious adverse events and adverse events related to the study procedure or the study device at 12 months.

3.3.3. Secondary Endpoints

The secondary endpoints for this trial are:

- Technical success;
- Freedom from limb loss on the study limb at 12, 24 & 36 months;

CONFIDENTIAL INFORMATION

MD133246 Protocol Template

Revision#: 1

Doc Type: GC

- Freedom from repeat intervention at 12, 24 & 36 months;
- Length of procedural hospital stay in days;
- Length of procedure in minutes;
- Serious adverse events and adverse events related to the study procedure or study device at 24 & 36 months;
- Primary patency at 24 & 36 months;
- Primary assisted patency at 12, 24 & 36 months;
- Secondary patency at 12, 24 & 36 months.

3.3.4. Listings

Listings of the following reported events will be provided:

All Endoleaks

Device Migration

Device Fracture

Major amputation on the study limb

Minor amputation on the study limb

4. Study Population

4.1. Description of Population

The study population includes patients with a symptomatic aneurysm or asymptomatic aneurysm (≥ 2 cm diameter) of the popliteal artery, or presence of mural thrombus (< 2 cm) in the popliteal artery. All patients treated per IFU with the GORE® VIABAHN® Endoprosthesis since September 15, 2012 (date of reimbursement in France) will be screened consecutively, starting with first treated patient.

4.2. Inclusion Criteria

Inclusion to the study requires the patient:

1. Received a GORE® VIABAHN® Endoprosthesis to treat a popliteal artery aneurysm
2. Had a symptomatic aneurysm or asymptomatic aneurysm (≥ 2 cm diameter) of the popliteal artery, or the presence of mural thrombus (< 2 cm) in the popliteal artery;
3. Was 18 years of age or older at the time of the treatment;
4. Had an elective popliteal artery aneurysm procedure;
5. Has provided Informed Consent, personally or through lawful representation as determined by applicable local regulations and state law (Section 5.2).

4.3. Exclusion Criteria

Prior to or at the time of implant the patient is / has:

1. Bilateral popliteal artery aneurysms with initial treatment on the same day;
2. Thrombotic occlusion of the popliteal artery or PAA
3. Marfan syndrome or Ehlers-Danlos syndrome;
4. Unable to tolerate antiplatelet therapy;
5. Thrombophilia requiring long term anticoagulation
6. Known allergies to the GORE® VIABAHN® Endoprosthesis components;

CONFIDENTIAL INFORMATION

MD133246 Protocol Template

Revision#: 1

Doc Type: GC

7. Enrolled in another investigational drug or medical device trial where participation may have affected the outcome or treatment of the subject in the popliteal artery aneurysm study with the GORE® VIABAHN® Endoprosthesis or had previous surgery for the popliteal artery aneurysm in the study limb.

4.4. Patient selection

For this Post-market study it has been decided that the screening of the patient records will start with patients treated September 15, 2012 and continuously go forward.

At each Site the Principal Investigator and his team will confirm in- and exclusion criteria for each patient and will contact the patient to obtain his agreement to collect medical data:

- a. If the patient meets the criteria and gives his agreement to participate he will be considered as enrolled.
- b. If the patient does not agree to participate or fails to meet the Inclusion / Exclusion criteria he will be considered as a screening failure and the reason will be documented in the Not Included Patient CRF.
- c. If the patient does not respond after three call attempts he will be considered as lost to follow-up and this will be documented in the Not Included Patient CRF.
- d. If the PI and his team are informed by the family during one of this calls that the patient previously died in another hospital they will inquire the reason and the date of the death. This will be registered in the Not Included Patient CRF. If the family refuses to give details only the death will be registered in the Not Included Patient CRF but no more details.

In case the PI and his team have clinical information available that patient died in their hospital cause and date of death will be registered and the Not Included Patient CRF will be completed.

CONFIDENTIAL INFORMATION

MD133246 Protocol Template

Revision#: 1

Doc Type: GC

5. Study Procedures / Evaluations

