5.12. Duration of Investigation

Each subject will be followed for approximately 36 months and then exit the investigation. It is anticipated that all patients will be enrolled within a period of nine months. The subject enrolment period is expected to occur from March 2015 to December 2015. The last subject primary endpoint follow-up is expected to occur by the end of 2017.

6. Study Administration

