9.1.3. Adverse Event Reporting and Coding

AEs will be reported on the appropriate CRF for that visit and documented in the subject's permanent medical record. The Investigator at each Site is ultimately responsible for reporting AEs to the Sponsor. The Investigator shall supply the Sponsor with any additional requested information.

Timely and complete reporting of safety information assists the Sponsor in identifying any untoward medical occurrence, thereby allowing: (1) protection of safety of study patients; (2) a greater understanding of the overall safety profile of the GORE® VIABAHN® Endoprosthesis; (3) appropriate modification of study protocols; and (4) adherence to worldwide regulatory requirements.

The following information should be collected for each reported AE:

- AE Name
- AE Onset Date
- Relationship
- Classification (serious / non-serious)
- Treatment
- Outcome
- Resolution Date

All reported AEs will be coded using the Medical Dictionary for Regulatory Activities (MedDRA).

In reporting AEs the following submission guidelines should be followed:

- AE reporting begins once the subject has received a GORE® VIABAHN® Endoprosthesis and continues until study completion / discontinuation.
 - NOTE: Any AE that occurs while the subject is in the operating room / catheterization laboratory should not be recorded as an AE, unless it is unresolved when the subject leaves the operating room / catheterization laboratory.
 - NOTE: Any AE occurring after the final study visit will not be recorded in this study.
- AEs with an outcome status of "Ongoing" should be assessed at each follow-up evaluation to determine if the event has resolved. AEs ongoing at study completion / discontinuation should be left as "Ongoing" on the AE CRF.

CONFIDENTIAL INFORMATION

MD133246 Protocol Template

Revision#: 1

Doc Type: GC

- Clinical sequelae present at baseline should be recorded on the Medical History CRF. If the clinical sequela increases in severity or frequency from baseline then it should be reported as an AE.
- If known, the diagnosis of the underlying illness or disorder should be recorded, rather than its individual symptoms. If unable to provide a diagnosis, report the symptoms as separate events. AEs should be reported using the full name without abbreviations or narratives.

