10.3.2. Analysis Populations

All enrolled Patients will be included in the analysis. Patients who have had bilateral PAAs treated with the GORE® VIABAHN® Endoprosthesis in both limbs will have only the data from the first limb collected in this study when the limbs were treated at different dates. Patients that had PAAs treated in both limbs on the same date will be excluded to avoid confounding issues with select endpoints.

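### Deaths before the 2015 consent contact cannot enter the 12-month safety counts, and no planned table counts them over all eligible treated patients

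*Protocol*

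**What the plan says.** **Start of safety time.** Protocol 9.1.3: "AE reporting begins once the subject has received a GORE® VIABAHN® Endoprosthesis and continues until study completion / discontinuation". The eligible implants begin on 15 September 2012.

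**Who is enrolled, and when.** Consent is an inclusion criterion (Protocol 4.2) and must be signed before data entry (5.2). Protocol 3.2: "Inclusion for all patients will be retrospective, follow-up visit(s) can be prospective". Protocol 5.12: "The subject enrolment period is expected to occur from March 2015 to December 2015". Enrolment goes in order from the first treated patient and stops once 50 have 12-month data (3.2, 5.4).

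**Deaths and silence before contact.** Protocol 4.4 covers three cases, and all go to the Not Included Patient CRF:
- Death at the site: when the team knows a "patient died in their hospital cause and date of death will be registered and the Not Included Patient CRF will be completed".
- Death elsewhere: date and reason are asked of the family, but "If the family refuses to give details only the death will be registered in the Not Included Patient CRF but no more details".
- No answer: "If the patient does not respond after three call attempts he will be considered as lost to follow-up".

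**Who is analysed.** Protocol 10.3.2 and SAP 5.2: "All enrolled Patients will be included in the analysis". The primary safety result is a tabulated count at 12 months (Protocol 10.3.4, SAP 5.4).

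**Planned output on deaths and non-included patients.** There are four items:
- a screen-failure summary with subject number, procedure date and reason (Protocol 5.4);
- a listing of reasons for non-inclusion (SAP 8.2);
- a Listing of Deaths whose coverage is not stated (SAP 8.2);
- a completion/discontinuation table with death as one exit reason (SAP 8.1).

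**The concern.** A patient's first-year safety record is counted only if that patient is alive, reachable and consenting at a contact that may come more than two years after implant. A patient who died in that first year, before contact, is removed from both numerator and denominator. This happens when the plan is followed exactly, so the bias controls in Protocol 10.4 and SAP 5.6 (adherence and monitoring) do not touch it.

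The study sets out to document safety, and its primary safety result is a simple count in about 50 patients. A fatal-event count of zero or near zero could then come from the way patients are selected, and nothing in the planned tables would let a reader tell. Neither document says that results are conditional on survival to contact.

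**Working it through.** The documents give no mortality rate, implant dates or number of eligible treated patients, so there is no stated figure to reproduce. The dates are given; the rest is assumption, shown as a range.

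**1. Dates.** From 15 September 2012 to 1 March 2015 is 897 days; to 31 December 2015 is 1,202 days.

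**2. Share of first-year patient-time that precedes contact.** This approximates the share of first-year deaths if the death rate is roughly constant over the year. For one contact date T days after the window opens, average min(time from implant to contact, 365)/365 over implant dates up to T. With a = 365/T:
- even implants: 1 − a/2
- linearly rising: 1 − a + a²/3
- quadratically rising: 1 − 3a/2 + a² − a³/4

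| Implants | T = 897 | T = 1,202 |
|---|---|---|
| Even | 79.7% | 84.8% |
| Linear rise | 64.8% | 72.7% |
| Quadratic rise | 53.8% | 63.0% |

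Simulations with contacts spread over the enrolment period, or made in implant order, and implants spread over 1.5 to 3.29 years give 80–100% (even) and 65–100% (linear). If all enrolled patients were treated by 1 March 2014 (day 532), then 897 − 532 = 365 and the share is 100%.

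**3. The case that breaks 'most'.** Let implants run to 31 December 2015, with earlier patients contacted on 1 March 2015 and later ones consenting at implant:
- even: (897 − 182.5)/1,202 = 59.4%
- linear: (897/1,202)² × 0.648 = 36.1%
- quadratic: (897/1,202)³ × 0.538 = 22.4%

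With first contact on 14 July 2015 (T = 1,032) these become 70.7%, 50.7% and 36.9%.

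**4. Number missed per 50 eligible patients.** The answer depends on which events count. Protocol 3.3.1 and SAP 2.3.1.2 restrict adverse events to those related to device or procedure. The opening of Protocol section 9 defines them whether or not related. Under either, a death enters only through its underlying event (Protocol 9.1.4).
- *All events.* 50 × assumed 12-month mortality × share of 0.65 to 1.00: about 1.0–1.5 at 3%, 1.6–2.5 at 5%, 3.3–5.0 at 10%.
- *Related only, assuming related deaths fall in the first 30 days.* With T = 897 and b = 30/897, the share before contact is 1 − b/2 = 0.983 (even) or 1 − b + b²/3 = 0.967 (linear). Then 50 × 0.5% / 1% / 2% × (0.967 to 1.00) gives about 0.24–0.25 / 0.48–0.50 / 0.97–1.00.

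**5. Effect on the reading.** Suppose 60 eligible patients, 5% 12-month mortality, 80% of deaths before contact and 10% non-consent among the rest. True deaths are 3.0. Never enrolled: 3.0 × 0.8 = 2.4. Countable: 0.6 × 0.9 = 0.54. Enrolled: (60 − 2.4) × 0.9 = 51.8. Apparent mortality is 0.54/51.8 = 1.0% against a true 5%.

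For scale, the exact 95% interval for 0/50 is 0–7.1%. One added death gives 1/51 = 2.0% (0.05–10.45%); three give 3/53 = 5.7% (1.2–15.7%).

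**The case against.** The strongest reply is that the plan already records these deaths. Protocol 4.4 asks for cause and date, the Protocol Summary collects intervention date and reason for non-inclusion, and the SAP plans listings. With perhaps one to five deaths at stake, a listing could show every case. That stands as to data collection, and it makes the fix cheap. It does not supply what is missing: the Listing of Deaths is not said to cover non-included patients, the screen-failure summary carries no date of death, the discontinuation table is not tied to 12 months, and none has a denominator of treated patients.

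Second, the selection follows from the consent rule, and mortality is not a named endpoint. Both are true. The fix therefore leaves selection and the endpoint alone and adds a supportive table.

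Third, some first-year follow-up may be prospective. Protocol 5.12: "The last subject primary endpoint follow-up is expected to occur by the end of 2017". This stands. A patient who consents before month 12 and then dies is analysed, so a reader who infers that every first-year fatal event is lost goes too far. Nor do the documents support the claim that most are lost under any implant pattern; step 3 of the working gives counter-cases. Those need rising implants to late 2015 with consent at implant, which sits poorly with retrospective inclusion of all patients, earliest first, stopping at 50.

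Finally, the design schema (Protocol Figure 3) is not shown, so it may already depict part of a patient flow.

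**Conclusion.** The concern holds for mechanism and direction. First-year fatal events before contact cannot enter the primary safety counts, and the counts err toward too few. That these are probably most such events is an inference from the dates: about 65–100% under even or linearly rising implants, and still above half under a quadratic rise when inclusion is retrospective.

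The number missed is not known. On assumed rates it is probably at most about one per 50 under the related-only wording, though nearly all such deaths if they occur early, and it could be several under the broader wording. The two definitions must be reconciled before the count can be interpreted.

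A reader might also infer that patency is biased in a known direction. The documents do not settle that. This should be fixed, but as a matter of reporting, without redesign. Confidence is high for the direction and low for the size.

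**What to change.** 1. **Supportive table beside primary safety (SAP 5.4, 8.1).** Tabulate known deaths within 365 days of implant, with cause where known.
   - *Denominator:* all patients treated from 15 September 2012 up to a stated cut-off who met every criterion except consent or contact. One possible cut-off is the implant date of the last enrolled patient at each site.
   - *Source:* enrolled patients' data plus the Not Included Patient CRF.
   - *Statistics:* an exact 95% interval, the number with unknown vital status or date of death, and bounds counting these as alive and then as dead.
   - *Relationship:* it is not collected for non-included deaths, so show it only where the recorded cause allows a judgement, and otherwise as unknown.
2. **Listings and flow.** State that the SAP 8.2 Listing of Deaths includes non-included patients. Extend the Protocol 5.4 screen-failure summary to a treated-to-enrolled flow with reasons.
3. **Interpretation.** State that enrolled-only safety and patency results are conditional on survival to contact and consent.
4. **Definitions.** Reconcile Protocol 3.3.1 and SAP 2.3.1.2 with the opening of Protocol section 9.

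**Cost.** SAP text, one clarified item on the Not Included Patient CRF (eligible apart from consent or contact), and an amendment submission to CCTIRS and CNIL (Protocol 6.5), whose acceptance is not a formality for people who did not consent. The supporting figures will look less favourable and the bounds may be wide. As an invented example, 50 enrolled survivors, 3 known deaths and 5 patients of unknown status give 3/58 = 5.2% (1.1–14.4%) to 8/58 = 13.8% (6.15–25.4%).
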